4 STUDY PRODUCT AND ADMINISTRATION

Specific product information is provided in each vaccine-specific appendix.

4.1 For a description of Adacel and Boostrix, please see Appendix A.

For a description of Fluzone High-Dose, please see Appendix B.

For a description of Bexsero for Meningococcal serogroup B and Nimenrix, Menactra, and Menveo for Meningococcal serogroups ACWY, please see Appendix C.

For a description of Avaxim, Havrix and Vaqta for Hepatitis A, Engerix-B and Recombivax for Hepatitis B, Twinrix for combination Hepatitis A and B, Typherix, Typhim Vi and Vivotif for Typhoid Fever, and ViVaxim for combination Hepatitis A and Typhoid, please see Appendix D.

For a description of Shingrix and Zostavax II for Herpes Zoster, please see Appendix E.

5 ETHICAL AND REGULATORY CONSIDERATIONS

5.1 Informed Consent Process and Documentation

This study will be conducted in accordance with all Research Ethics Board requirements. The protocol and all related materials will be submitted to the local independent Research Ethics Boards of the Canadian Center for Vaccinology, Halifax (Nova Scotia Health Authority provincial Research Ethics Board, and Horizon Health REB in New Brunswick), and the Child and Family Research Institute (CRFI), Vancouver (they will be responsible for data management for the AEFI survey only) for review and approval. If the survey is administered in other provinces, it will be submitted to the appropriate REBs. All REBs are constituted in conformance with the Canadian Food and Drug Act and Regulations (C05.005, C05.006). A copy of the REBs' letters of approval for the study will be kept.

No changes will be made to the protocol without REB approval. Pharmacists/pharmacies will be able to withdraw their participation from the study at any time without giving a reason.

Participating Pharmacies

For the pharmacy intervention, the participants are the pharmacies that agree to carry out the study intervention rather than members of the public. Pharmacies will be able to withdraw from the study at any time.

General Public and Healthcare Providers' KABB

Survey participants will receive an information sheet providing them with information about the survey prior to completing the online survey. A consent statement will be included as the first question of the survey. An affirmative answer will be required to proceed with the survey. The participants will be notified that they can withdraw from the study at any time until the survey is submitted. Completion of the online survey implies consent. Surveys are anonymous and participants will not be able to withdraw once they have submitted their questionnaire as the survey instrument cannot be traced back to the original participant.

Adverse event following immunization survey

An information sheet will be provided to influenza vaccine recipients and participants will be required to indicate their consent on the introductory page of the online survey in order to proceed to the survey.

6 OUTCOME MEASURES AND STATISTICAL METHODS

6.1 Outcomes/analysis plan/sample size/statistics

6.1.1 Primary Outcomes

- 1. Population specific vaccine coverage before and after bundled pharmacist-delivery intervention.
- 2. Proportion of population in intervention districts whose supplementary health benefit plans cover studied vaccines.
- 3. Public KABB about vaccine preventable diseases and related vaccines before and after program implementation interventions.
- 4. Public willingness to pay and co-pay for studied vaccines.
- 5. Health care KABB regarding pharmacist- delivered vaccine programs.
- 6. Public and health care provider satisfaction with various models of vaccine program delivery.

ROMEO File #: 1021559

Proportions of influenza vaccine recipients who register for CANVAS and who complete the online AEFI survey in intervention versus control communities.

6.2 Analysis Plan, Statistics and Sample Size

1. KABB Surveys. Although the response rate is expected to be higher, surveys returned from 400 individuals will provide a 95% confidence interval of \pm 5% around the point estimate for any survey question. The first level of analysis will comprise a review of descriptive statistics for trends in the data. The second level of analysis will involve tests of association. Continuous variables will be presented as summary statistics (i.e., mean and standard error) and categorical variables by frequency distributions (i.e., frequency counts, percentages and their two-sided 95% exact binomial confidence intervals). Descriptive statistics will be used to estimate the proportion of respondents who answered correctly the knowledge-based questions and who had specific attitudes towards and beliefs about studied vaccines. Differences in survey responses between groups will be assessed using Fisher's exact tests. For continuous predictors, logistic regression will be used. Overall knowledge scores will be compared using t-tests. Associations between attitude questions, behavioral responses and demographics will be estimated using ordinal logistic regression or Fisher's exact tests. P-values < 0.05 will be considered statistically significant. If the data support further analysis, demographic and population characteristic variables will be used to develop predictive models for knowledge and attitude responses. Logistic regression will be used to predict binary knowledge responses, in which the model is used to predict the probability of agreeing or disagreeing with the associated statement. Ordinal logistic regression will be used to predict ordered attitude responses, where the model is used to assess the degree (strongly disagree, disagree, neither agree nor disagree, agree, strongly agree) to which subjects have knowledge regarding particular issues. The particular ordinal logistic regression model to be fit is a cumulative logit model. For each outcome variable, whether binary or ordered, the collection of demographic and population characteristic variables will be used in a backwards elimination stepwise procedure to develop a multiple regression model. Those predictor variables remaining at the termination of the stepwise procedure are summarized, and p-values are indicated. P-values of <0.05 will be considered statistically significant. If the number of survey respondents $N \ge 400$, then the estimated proportion of the "yes" response to any fixed KABB survey item will have margin of error <.05.

2. AEFI Surveys. Point estimates and exact binomial 95% confidence intervals will be calculated for the proportion of influenza vaccine recipients who register for the AEFI survey and the proportion who complete the survey. Descriptive statistics will be used to compare proportions registering and completing the survey among intervention versus control communities. Overall frequency of severe adverse events and the frequency of specific health events (e.g., injection site pain that prevents daily activities) will be calculated. The frequency of severe AEFI will be compared by influenza vaccine type [e.g., QIV, TIV] and by season (i.e., 2016-17 and 2017-18). The frequency of health events after vaccination will be compared to the background event rate estimated by the control survey.

3. Vaccine coverage. Pharmacy databases will be used to determine the number of doses administered to individuals eligible for receipt of vaccine relative to the total number of clients in the pharmacy database in the eligible age range. A second estimate of coverage will be

ROMEO File #: 1021559

determined by physician billing data and public health provision of vaccine to physicians relative to the Statistics Canada population age specific census data for that community. A study-specific system of reciprocal notification forms for family doctors will be implemented that is similar to that used for publicly funded routine vaccines. A third estimate of vaccine coverage will be vaccine doses distributed in the participating communities (obtained from the manufacturer) relative to the eligible population based on Statistics Canada census data (2011 and 2016 when available). The fourth estimate of vaccine coverage will be derived from the pre- and postprogram public survey. Binomial point estimates and confidence intervals will be made for vaccine coverage rate within site, and coverage will be compared between and among sites using confidence intervals for the difference of binomial proportions, Fisher's exact tests, and logistic regression. Using a margin of superiority of 10%, when comparing two coverage proportions within site or between sites, a sample size of 298 per group gives 80% power to conclude in favor of superiority when the true difference in proportions is at least 20%, and a sample size of 1209 per group provides 80% power when the true difference in proportions is at least 15%, assuming independent responses. However, it is anticipated that there will be dependence within the family unit regarding the decision to be vaccinated, in which case the precision on the binomial point estimate, and thereby, the required sample size, depends on the size of the family unit and the intraclass correlation. Assuming the family unit to consist of two adults, and under the worst-case scenario in which the decision on vaccination is fully concordant for the two family members, the required sample size per group to detect a specified difference is doubled, to 596 (2418) when the true difference is at least 20% (15%). Estimates of the intraclass correlation will be calculated using data from pharmacy databases and from the public survey portion of the study, and these will be used to adjust confidence intervals and test statistics to accommodate within family dependence (Donner, Brikett, & Buck, 1981).

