Pharmacists in intervention communities will provide vaccines through bundling of different payment mechanisms and communication strategies, depending on the vaccine. Descriptions of the various methodologies used for the study are below.

Different Payment Mechanisms

Intervention communities will provide vaccine through the following payment mechanisms, based on the study vaccine:

- 1. universal vaccination with "publicly funded" vaccine (vaccine provided to individual without charge (i.e. Tdap vaccine))
- vaccination using a co-pay model (individuals receive vaccine at no cost after paying a designated co-pay fee comprised of the pharmacy dispensing fee and any administration fee charged by the pharmacist immunizers (i.e. highdose TIV); and
- 3. vaccination using the current private market model where vaccine would be purchased either by the recipient or through insurance (standard of care control arm, (i.e. Meningococcal serogroup B, Meningococcal serogroup

ROMEO File #: 1021559

ACWY, high-dose TIV influenza, travel health vaccines, and herpes zoster vaccine).

Different Public Communication Strategies

Pharmacists and pharmacy staff in intervention communities will use various public communication strategies, including:

- 1. targeted mail outs and/or phone calls by pharmacies to individuals in their databases based on risk factors for contracting and/or transmitting vaccine-preventable disease (e.g., immunosuppressant medications, recent birth in family)
- 2. timed marketing linked to other vaccine clinics (e.g., influenza clinics) and awareness campaigns (e.g., back-to-school advertising)

The non-intervention control arm will be the current model wherein a client specifically requests a vaccination or the pharmacist offers this option while the patient is in the pharmacy.

Outcome measure:

1. Repeated Cross-Sectional KABB

KABB will be determined by public surveys in the four communities and by surveys of health care providers (pharmacists, physicians, and public health practitioners) prior to and after the two-year intervention.

2. Vaccine Coverage

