2 OBJECTIVES

2.1 Primary Objectives

The proposed study has two primary objectives:

- 1. To assess the effectiveness of a bundled pharmacist-delivery strategy consisting of communication and funding strategies on vaccine coverage.
- 2. To determine the increase in pre- and post-intervention knowledge, attitudes, beliefs and behaviours (KABB) of target adults, pharmacists, physicians, and public health practitioners.

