2.2 Secondary Objectives

- 1. To assess the impact of various funding models on vaccination coverage.
- 2. To evaluate a pharmacy-based strategy for recruiting participants for a patient-reported active adverse event following immunization surveillance system.

2.3 Primary Hypothesis:

 Vaccine coverage with all studied vaccines (high dose TIV, meningococcal B vaccine, meningococcal ACWY vaccine, Tdap, herpes zoster vaccine, and travel health vaccines) will increase significantly after implementation of the bundled pharmacist-delivery strategy. A significant increase will be defined as an increase of ≥10% vaccine coverage from preintervention levels.

2.4 Secondary Hypotheses:

- 1. The cost of a vaccine is a key factor in the individual's decision to be vaccinated. It is expected that vaccinations provided at no or minimal charge will have higher uptake than those that require more financial resources to obtain.
- 2. Knowledge about the vaccines studied is low among the general public, but higher among practitioners. There is a high level of support among both the public and health care providers for pharmacists as immunizers. Knowledge and support amongst both providers and the public will increase after implementation of the program.

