The health belief model (HBM) was developed in the 1950s by social psychologists in the U.S. Public Health Service in an attempt to understand the common failure of people to accept disease preventives or screening for the early detection of disease (Edberg, 2010). According to the model, engagement in health action rests on the belief that such action can reduce a threat that is both likely and would have severe consequences (Glanz, 2015). The constructs that predict whether and why an individual will take action to prevent, detect or control illness conditions according to the HBM, include perceived susceptibility, severity, benefits and barriers to engaging in health actions, cues to action, and self-efficacy (Glanz, 2015).

There is considerable correlation between the HBM and the theory of planned behaviour (TPB) proposed by Ajzen and Timko (1986). Both theories are based on the same framework, make similar assumptions, have overlapping constructs and adopt an individual level approach to predicting health behaviour. The primary difference between them is that the TPB contains a proximate predictor of behaviour or an intention to act, where the HBM does not (Gerend, 2012). The combination of both of these theories is beneficial to this study because it will allow a broad understanding of the intent to vaccinate in addition to vaccine-specific perceptions of barriers and facilitators that will help focus future intervention. A blended TPB and HBM survey design from a 2014 study led by the Vaccine Evaluation Center along with members at the Canadian Center for Vaccinology (Schneeberg, 2014), will inform the selection of questions for the proposed survey in addition to relevant literature.

Survey Design and Study Population

This study will use repeated cross-sectional online surveys to assess the KABB of community-dwelling adult members of the public regardless of whether or not they were vaccinated as part of this study and a second survey for physicians, pharmacists, and vaccine providing nurses. Surveys will be distributed before and after the intervention regarding knowledge, attitudes, beliefs, and behaviours of targeted vaccines and their delivery by pharmacists.

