For the community public surveys, all individuals >18 years of age in the intervention and control communities in Nova Scotia and New Brunswick will be eligible regardless of whether or not they were vaccinated as part of this study. Adult residents in all four participating communities will be informed about the survey and invited to participate by means of local advertisements in community print and online publications, posters, via social media, and through information distributed in the community pharmacies. These advertisements will contain the web address where the online KABB survey can be found.

ROMEO File #: 1021559

For the healthcare provider survey, all family physicians, pharmacists and vaccine providing nurses in Nova Scotia and New Brunswick will be eligible. In order to increase national generalizability, we will examine the logistics of partnering with investigators in other provinces to administer the surveys in their jurisdictions. Pharmacists and vaccine providing nurses in all four participating communities will be informed about the survey and invited to participate by means of local advertisements in print and online publications distributed by professional associations (such the Neighborhood Pharmacy Association) via available social media (e.g. Facebook groups and Twitter accounts with permission), posters on internal bulletin boards in local hospitals, and other publicly available means such as targeted outreach via email (e.g., publicly posted email addresses for clinics, pharmacies, etc.). Locally, physicians will be recruited for the KABB survey through the regional hospital medical staff offices. Provincially, physicians will be recruited through Doctors Nova Scotia. These advertisements will contain the web address where the online KABB survey can be found.

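### No planned KABB analysis estimates how far public responses change in the intervention communities beyond the change in the control communities

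*Combined protocol and SAP*

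**What the plan says.** Primary objective 2 (section 2.1) is: "To determine the increase in pre- and post-intervention knowledge, attitudes, beliefs and behaviours (KABB) of target adults, pharmacists, physicians, and public health practitioners". Section 2.4 predicts: "Knowledge and support amongst both providers and the public will increase after implementation of the program".

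On who is surveyed, the synopsis states: "KABB will be determined by public surveys in the four communities and by surveys of health care providers". Section 3.2 makes eligible for the public survey "all individuals >18 years of age in the intervention and control communities", and describes the design: "This study will use repeated cross-sectional online surveys to assess the KABB of community-dwelling adult members of the public". The public survey therefore gives four independent sets of respondents: intervention and control, each before and after. Provider eligibility in section 3.2 is wider, covering the family physicians, pharmacists and vaccine-providing nurses of both provinces.

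Section 3.1 gives the control communities their purpose, which is to be compared with the intervention communities when judging the bundled strategies. Section 8.2 calls a change in KABB an outcome measure of the study.

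The KABB analysis is in section 6.2 item 1. For item responses: "Differences in survey responses between groups will be assessed using Fisher's exact tests". For scores: "Overall knowledge scores will be compared using t-tests". It also names logistic regression for continuous predictors, ordinal logistic regression or Fisher's tests for associations among attitudes, behaviours and demographics, and, if the data allow, logistic and cumulative logit models built by backwards elimination from demographic and population characteristics. No arm, wave or arm-by-wave term is named there, or for KABB anywhere else. The only sample size statement for KABB is the precision of a single proportion from 400 respondents.

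**The concern.** A controlled before-and-after survey is run to separate a change due to the program from a change that would have happened anyway. That takes all four cells at once. Each test in 6.2 uses two:

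- A pre-post test in the intervention communities credits the program with any trend that the control communities share over the two years.
- A post-program test between arms credits the program with any difference that already existed between communities. Sections 3.1 and 3.2 describe no random allocation that would make such differences a matter of chance.
- Finding one arm significant and the other not is not a test of the difference between them.

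Because the groups are undefined, the choice between these contrasts could also be made after the data are seen. At stake is whether a reported rise in public knowledge or support may be called an effect of the pharmacist program.

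**Working it through.** **1. The plan's own figure.** Half-width for one proportion at 50% with n = 400: 1.96 × √(0.25/400) = 4.9 points. The stated ±5% reproduces. It is a one-sample figure and supports no contrast between arms or waves. Section 6.2 does not say whether 400 is per community, per arm, per wave or in total, so cells of 400, 200 and 100 are used below as assumptions.

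**2. Shared drift, no program effect.** Assume 50% before the program and the same rise in both arms. The drift is an assumption, and so is a two-sided 5% level. For 10 points and 200 per cell, SE = √[(0.50×0.50 + 0.60×0.40)/200] = 0.0495 and 0.10/0.0495 = 2.02, so the normal approximation gives Φ(2.02 − 1.96) ≈ 0.52. Fisher's test is somewhat conservative. Enumerating it exactly gives the chance that the pre-post test in the intervention arm is significant:

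| Shared drift | 200 per cell | 400 per cell |
|---|---|---|
| 5 points | 15% | 27% |
| 10 points | 48% | 79% |

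Simulations agree: 15% and 28% for 5 points, 46% to 49% and 79% to 80% for 10 points.

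**3. Baseline gap, no program effect.** With 400 per cell and an existing difference between arms of 5 (10) points, a post-program Fisher test between arms is significant in about 27% (80%) of simulated trials.

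**4. The arm-by-wave contrast.** The estimate is (post − pre, intervention) − (post − pre, control). Simulated at 400 per cell under steps 2 and 3, it is significant in about 5% of trials, provided all communities drift alike.

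**5. If communities drift differently.** There are two communities per arm. Let each community's drift have standard deviation s, with equal numbers of respondents per community. The sampling variance of the contrast with a 10-point mean drift is 2 × (0.25 + 0.24)/n. Community drift adds 2 × s²/2 = s². At n = 400 and s = 5 points: 0.00245 + 0.0025 = 0.00495. The true SE is then √(0.00495/0.00245) = 1.42 times the one used, and the false-positive rate is 2 × [1 − Φ(1.96/1.42)] ≈ 17%. At s = 3 points it is about 9% (10% by simulation). At n = 200 the rates are about 7% (s = 3) and 11% (s = 5). The values of s are assumed.

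**6. Precision after the change.** Near 50%, SE = √(4 × 0.25/n). The detectable change at 80% power is (1.96 + 0.84) × SE.

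| n per cell | 95% half-width | Detectable net change |
|---|---|---|
| 400 | ±9.8 points | 14.0 points |
| 200 | ±13.9 points | 19.8 points |
| 100 | ±19.6 points | 28.0 points |

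An illustrative 10-point net change needs about 785 per cell, against about 393 per group for a plain two-group difference. These figures ignore clustering by community, so real precision is worse.

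**The case against.** The strongest reply is that objective 2 is worded as a pre-post increase, unlike objective 1, which asks about effectiveness. The comparison of communities in section 3.1 also sits in the coverage part of the design. On that reading a pre-post contrast is what was promised. This stands as far as the wording goes: a reader might infer that objective 2 itself demands an effect net of control, and it does not. The need arises once the change is attributed to the program, which is why control communities are surveyed twice.

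Four other strong readings fail:

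- A reader might infer that 6.2 plans nothing beyond Fisher's and t-tests. It also names logistic, ordinal and cumulative logit regression. As written, these use demographic and population characteristics, so they leave the gap open but are the natural place to close it.
- A reader might infer that all KABB data divide by arm. Only the public survey does. Providers are eligible province-wide and many may belong to neither arm.
- A reader might infer that the control survey is useless. It still supports descriptive results and one of the coverage estimates in 6.2 item 3.
- A reader might add that Fisher's tests waste the ordering of Likert items. That is a separate, secondary matter, since 6.2 already allows ordinal regression for some associations.

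It is also fair to object that an arm-by-wave test does not guarantee 5%. With two communities per arm it does not, as step 5 shows. It still does much better there than the pre-post test does under a 10-point drift.

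**Conclusion.** The gap is real for the public survey. No planned analysis estimates the KABB change in the intervention communities beyond that in the control communities, and a pre-post increase alone cannot be credited to the program. With no program effect, the pre-post test would be significant in about 15% to 48% of trials at 200 per cell and 27% to 79% at 400. These sizes rest on an assumed shared drift of 5 to 10 points from 50% and on assumed cell sizes. A smaller drift gives a smaller error. The arm-by-wave contrast holds about 5% only if communities drift alike. For assumed community standard deviations of 3 to 5 points it runs at about 7% to 17%. The documents do not support extending the point to the provider survey, or saying that objective 2 as worded cannot be met. The plan should be changed, but this does not invalidate the survey.

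**What to change.** In section 6.2 item 1, for the public survey only:

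- Define the groups by arm and wave, and name the arm-by-wave term as the KABB program effect.
- Fit it by logistic regression for binary items, cumulative logit for Likert items and linear regression for the knowledge score. Each model has arm, wave, arm-by-wave, province, age group and sex, all forced in and exempt from backwards elimination.
- Report within-arm pre-post changes as descriptive.
- Show the change in each of the four communities, and so the net change within each province. State that with two communities per arm the individual-level interval understates the uncertainty.
- Keep provider KABB as a descriptive pre-post comparison unless respondents can be classified by study community.

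If only a descriptive pre-post change is intended, 6.2 should say so and make no claim of a program effect.

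The cost is plan wording and a few model statements. No extra respondents are required, but each public response must carry its community; surveys are anonymous, so the questionnaire has to record it. The price in precision is the wider interval shown above, which should be reported beside the ±5% now quoted.
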